4.3 Assignment of Test Treatment versus Placebo and Masking

Each intervention has its own placebo that matches the test treatment in mode of administration, color, size, and/or taste.

In the first two periods, each participant will receive a test treatment and its matching placebo, with the order being randomly determined (crossover sequence allocation). During subsequent treatment periods (periods 3-6), the placebo assignment probability is initially set to 0.17 but monitored throughout the study and adjusted as needed to yield, on average, approximately 25% of all participants receiving a second placebo. Once a participant receives a 2nd placebo, their probability of receiving placebo in subsequent periods is set to 0 (with some exceptions – see below). This strategy results in

participants enrolled earlier and therefore eligible for more treatment periods having a higher chance of receiving a second placebo than participants enrolled later in the trial.

If a participant discontinues treatment during periods 1 or 2 such that no post-baseline assessments of the FEV₁ percent predicted and ACQ-6 are available, the probability of their receiving placebo in periods 3 and 4 might be adjusted to ensure the participant will have efficacy evaluable data from at least one placebo period during the study. In period 3, the probability of receiving placebo = 0.5, and in period 4, the probability = 0 if placebo is received in period 3, and = 1 otherwise. The participant is also eligible to receive another placebo in periods 5-6 with the same probability as any other participant. A participant may therefore be randomly assigned placebo at most three times during the study and will contribute efficacy data to the statistical analysis from at most two placebo periods.

The initial randomization to a complete 2-period crossover design, with all participants receiving placebo during one of these two periods, allows for efficient estimation of treatment effects to support futility analysis of each test treatment early in the study. The addition of a randomly assigned second placebo allows for the estimation of time differences in placebo response and the potential to adjust the final efficacy analysis for any time trends observed. Because some participants will receive two placebos with different modes of administration (e.g., oral and injection or dietary and oral, etc.), we will also be able to estimate differences in placebo response between different administration modes.

The second placebo also provides some protection against expectation bias (relative to outcome assessments and other reporting behaviors) on the part of both the participants and the investigators/clinical staff, because there is a positive probability of placebo assignment in each treatment period for periods 3-6. Note also that to further maintain masking in periods 3-6, a subject can get a placebo matched to intervention A only if the subject has not yet received intervention A, and a subject who has completed a period with placebo matched to intervention A is not eligible to receive intervention A for the remainder of the study.

Using simulated data for the 2-step randomization scheme described above, we tabulated the number of periods between each active period (in periods 3-6) and the closest placebo period assuming a 16-week treatment period and 8-week washout (all interventions except clazakizumab). As can be seen from the results shown in Table 4 below, active and placebo periods will be adjacent 36% of the time, have one period between them 38% of the time, and separated by three or more periods (more than one year) only 9% of the time.

Table 4. Distribution of Time between Active Periods and the Closest Placebo Periods for Periods 3-6

0 periods	1 period	2 periods	3 periods	4 periods
0 years	0.46 years	0.92 years	1.38 years	1.87 years
36%	38%	17%	7%	2%

5. Power and Sample Size

An intervention is considered efficacious if significant benefit is shown for either of the two primary endpoints (FEV₁, or asthma symptom control score). Because there are multiple chances for an intervention to demonstrate efficacy, multiplicity adjustments are required. We will use the Hochberg method to adjust for multiplicity. According to the Hochberg method, the treatment is declared effective if the treatment-placebo comparison is significant at level α for both outcomes or it is significant at $\alpha/2$ for at least one of the outcomes.

A sample size of 111 participants for each intervention is required to achieve at least 80% power to detect a treatment effect with respect to at least one of the two primary endpoints equal to 0.3 times the standard deviation (SD) of that outcome, taking into account the possibility of stopping for futility with a non-binding stopping rule. If participant accrual in the target subgroup of one or more interventions is such that an interim futility analysis is not possible or practical (e.g., the study will conclude before the recommendations of the interim futility analysis can be implemented), the interim analysis will not be performed. In this case, 93 participants (2:1 ratio of biomarker positive to negative participants) are required to provide similar power for the final analysis.

All participants randomized to an active intervention or matching placebo will be included in the final efficacy analysis, but only participants who do not withdraw from the study prior to the start of period 2 are counted towards the required total sample size in estimating power. We also assume that about 10% of participants will discontinue an active treatment period soon after randomization in the power calculations. Attrition is monitored throughout the study, and the required sample size may be adjusted, if the treatment discontinuation rate is different from 10% or discontinuations occur later in the treatment period. This adjustment, if needed, will take place prior to any unmasking of treatment assignments, that is, prior to the interim futility analysis or, if the futility analysis is not feasible for an intervention, prior to the final analysis.

The Type I error probability will be controlled under the global null hypothesis (no effect on either endpoint) at $\alpha \leq 0.10$ two-sided. Power was estimated under the assumption of a within-participant, between-period correlation of responses in consecutive placebo and test treatment periods of 0.70.

Examples of treatment effects yielding a 0.3 standardized effect size include: a difference of 4.3 percent predicted FEV₁ between intervention and placebo with a SD of 14.5 percent predicted; and a difference of 0.18 in average ACQ-6 symptom scores between the intervention and placebo with a SD of 0.6.

Our analysis method ensures strong control of the Type I error probability at $\alpha = 0.10$ two-sided for each intervention. This value was chosen to reflect the experimental nature of this phase 2 proof-of-concept study. Taking into account both our stopping rule for futility and the Hochberg method for controlling multiplicity due to multiple primary endpoints, the Type I error probability is expected to equal about 0.05. Interventions that demonstrate evidence of efficacy in PrecISE with respect to at least one of the two primary endpoints may be studied further in a more fully powered phase 3 trial to provide substantial evidence of efficacy, controlling the Type I error probability at the more usual level of 0.05. Information learned from PrecISE regarding the optimal target subgroup for the intervention should be useful in developing an enrichment strategy for such a study.

No adjustment for multiplicity with respect to the multiple interventions in the study is planned. Success is defined independently for each intervention, and interventions will not be compared to each other in the efficacy analyses.

We are planning to enroll 395 participants. Assuming a study withdrawal rate of 2% a month, we anticipate that each participant will contribute data to two active interventions on average. This will allow us to accumulate required number of active treatment periods to test efficacy in all five interventions.

6. Data Sources, Documentation, and Verification of Results

6.1 Clinical Data Entry and Management in CDART

Clinical data are entered at each study site on electronic case report forms (eCRFs) using the Carolina Data Acquisition and Reporting Tool (CDART), a proprietary web-based data management system (DMS)

developed and maintained by the Collaborative Studies Coordinating Center (CSCC) in the Department of Biostatistics at the University of North Carolina at Chapel Hill. CDART incorporates robust security features, such as authentication log-ins, granular permissions based on user requirement, and encrypted data transmission to protect personal health information (PHI). CDART is compliant with the United States Food and Drug Administration's (FDA) 21 Code of Federal Regulations (CFR) Part 11 guidance (an audit report dated July 2021 confirming 21 CFR Part 11 compliance is available upon request from UNC's Office of Clinical Trials).

Real-time data edits are performed at the time of data entry that include range checks, consistency checks, and routing or skip pattern checks. Cross form checks and other algorithmic data queries are programmed for post-data entry checking in both CDART and SAS and. All SAS queries are sent to the sites for resolution biweekly, and sites are encouraged to run query reports from within CDART at least weekly. Customizable data reports are generated from within CDART (e.g., calendar scheduling for follow-up visits, enrollment reports, etc.). Additionally, data summaries are available through a web-based dashboard with views for report generation outside of CDART (e.g., outstanding query reports by site).

To facilitate data sharing, CDART conforms to the Clinical Data Interchange Standards Consortium (CDISC) Operational Data Model (ODM) standard. The ODM was designed to support electronic acquisition, exchange and archive of electronic data and meta-data in a standard XML-based format. The ODM defines structures to represent clinical study metadata, clinical study administrative data and clinical study patient data. CDART allows automated data extraction using a RESTful API to provide data and meta-data to authorized callers. SAS and other analysis software packages can easily process the files to define datasets and populate them with study data.

All tables, data listings, and graphical displays summarizing PrecISE study data and all statistical analyses described in this analysis plan will be generated using SAS Version 9.4 or higher (SAS Institute, Cary, NC) and the R language.

Data summaries and analysis results are verified prior to release through the following steps:

- Programs for producing created variables and analysis files; programs for generating data summaries, data listings, and graphical displays; and programs for conducting statistical analysis models are fully specified by project statisticians prior to programming
- Program output is reviewed and verified by comparing against the analysis specifications
- Independent validation is then conducted by team members not involved in the original specifications, for primary and key secondary analyses

6.2 External Data Transfers

Datasets generated from outside vendors are transferred via secure file transfer protocol (FTP) to the PrecISE coordinating center. The data are loaded into the CDART system using an 'Extract, Transform, Load' process. During the load step the data are validated. Any errors in data type, value or expected record structure are reported to the external vendor. External files include data from the central laboratories (PPD and Labcorp), e-diary data (symptoms, controller medication adherence, peak flow) from Propeller Health, data from CT scans of the lung, spirometry data for the assessment of lung function from Vyaire and MIR, results from sputum analyses, and results of other biospecimen analyses. Periodic transfers of data from the respective cores, reading centers, or vendors for each of these sources are processed, and quality control checks performed for data completeness and accuracy. Queries based on comparisons of data from the external data sources and data entered on eCRFs at the clinic are generated, where appropriate, and sent to the sites for resolution. Additional queries to

confirm appropriate follow-up at the clinical sites, when called for, based on external data values (e.g., abnormal lab values) are also generated as quality control checks.

6.3 Pandemic-Related Changes in Data Sources

To accommodate the event of a clinic shutdown during the study, a spirometer that could be used in the home was incorporated for acquisition of lung function data. The study began with the Vyaire spirometer for in-clinic assessments. During the first year of enrollment, participants were provided a MIR spirometer for use in the home. A pilot study was conducted to compare results from the two spirometers, and based on these results, the DSMB approved a switch to the MIR spirometer for assessing lung function at all study visits. The first and last visit in each treatment period (Visit X.1 and X.5 for period X) are to be conducted with the MIR spirometer in the clinic, and all other visits may use in-clinic or home spirometry at the discretion of the site coordinator, with two exceptions. Note that patients who began the study using the Vyaire spirometer will not switch for their current or any future treatment periods. The methacholine challenge and maximum BD response assessments are to continue to be assessed during screening using the Vyaire spirometer in the clinic. In the event of a clinic shutdown, the Visit X.1 and X.5 spirometry maneuvers are to be conducted in the home using the MIR spirometer already assigned to the participant.

7. Statistical Analyses

7.1 Analysis Populations

Screening Population: Participants who are screened but not randomized will be reported, but not included in any efficacy or safety analyses of study data. SAEs occurring during the screening period are monitored and reported to regulatory agencies each month and will be summarized in final study reports.

Safety population: The Safety population for each intervention consists of all participants randomized to that intervention (active or placebo) who received at least one dose of study medication. This population will form the basis for all safety analyses and selected secondary efficacy analyses of the intervention.

Intention-to-Treat (ITT) Population: The ITT population for each intervention will consist of all participants randomized to that intervention. Participants in the ITT population who are also in the target subgroup for an intervention (in either the a priori target subgroup or in the biomarker negative subgroup) will form the basis for the interim futility analysis.

The primary and secondary efficacy analyses will be conducted using a modified intention-to-treat (mITT) population. The mITT population for an intervention consists of participants who are randomized to the intervention, receive study drug, and contribute at least one post-baseline measurement for each of the primary endpoints during the treatment period in which the participant is randomized to the intervention.

Per-Protocol Population: The per protocol population for each intervention consists of all participants in the mITT population who complete study treatment and are in reasonable compliance with the protocol during the treatment period in which the participant received the intervention. For per protocol analysis purposes, we define compliance as:

- For MCT, clazakizumab, Broncho-Vaxom and cavosonstat, the per-protocol population will include participants completing at least 14 weeks of treatment. In addition, the percentage of intended dose of the study drug taken over the course of follow up is at least 60% for MCT, at

least 75% for clazakizumab (at least 3 out of 4 injections), and 90% for Broncho-Vaxom and cavosonstat.

- For imatinib, the per-protocol population will include participants completing at least 8 weeks of treatment and the end of treatment visit. Additionally, participants should have reached the target dose of 400 mg at least 4 weeks before the end of treatment.

Membership in the per protocol population will be determined prior to unmasking of treatment assignments to avoid the potential for bias. This population will form the basis of selected secondary analyses.

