### ***Intention-to-Treat (ITT) Population***

The ITT population for each intervention will consist of all participants randomized to that intervention.

The primary and secondary analyses will be conducted using the modified intention-to-treat (mITT) population, where a participant receives study drug (test treatment or placebo) and contributes at least one post-baseline measurement for each of the primary clinical endpoints during the treatment period in which the participant receives the intervention.

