An intervention will be considered beneficial if it demonstrates improvement with respect to either of the two primary endpoints relative to placebo. See Section 3 for details about assessments for each of the primary and additional secondary endpoints.

Summaries of the questions of interest and descriptions of the estimand attributes are shown in Table 2, following the framework provided in the International Council on Harmonisation (ICH) guideline, E9(R1).³

Table 2. Study Objectives and Estimands for FEV₁ percent predicted, ACQ-6 and CompEx

Question of Interest	Objective Description / Study Population	Endpoint(s)	Intercurrent Events	Population Summary
Does Intervention A improve lung function compared to placebo, for patients suffering from severe and/or exacerbation-prone asthma?	Primary objective of the study / All randomized participants receiving Intervention A during any study period	FEV ₁ percent predicted assessed prior to bronchodilation	For analyses of FEV ₁ percent predicted, intercurrent events include (i) asthma exacerbations (protocol Section 6.5.3), (ii) major change in therapy (protocol Section 6.5.4); and (iii) treatment discontinuation due to adverse events or lab abnormalities (protocol Section 7.1). Note that study discontinuation when outside of a treatment period is not an intercurrent event, as each new treatment period is associated with a new randomization for treatment assignment.	Mean difference in FEV ₁ between test treatment and placebo and its associated confidence interval from a mixed model for repeated measurements (MMRM). Positive values indicate a benefit of Intervention A.

Does intervention A improve asthma symptom control compared to placebo, for patients suffering from severe and/or exacerbation-prone asthma?	Primary objective of the study / All randomized participants receiving Intervention A during any study period	6-item score from the Juniper Asthma Control Questionnaire (ACQ-6)	For analyses ACQ-6, intercurrent events are defined identically to those defined for FEV ₁ percent predicted.	Mean difference in ACQ-6 between test treatment and placebo and its associated confidence interval from a MMRM. Positive values indicate a benefit of Intervention A.

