7.3 Unblinding for Interim and Final Analyses of Each Intervention

Both interim and final analyses for each intervention are conducted independently of other interventions, consistent with the master protocol design. Statistical analyses for Intervention A are based on participants randomized to Intervention A during the trial. The treatment periods in which participants were randomized to A plus matched placebo periods contribute to the analysis. For participants without a matched placebo, all placebo periods will be included in the analysis. For analyses based on the mITT and per protocol populations, the treatment periods included in the analyses are limited to those satisfying the respective mITT and per protocol criteria stated above. Other treatment periods from the participant might be used in the analysis to estimate the within-participant correlation in the crossover if the primary model does not converge.

The target sample size for the interim analysis of Intervention A, with objective to test for futility, is 34 biomarker positive participants and 17 biomarker negative participants.

Once an intervention achieves the target sample size for an interim analysis, an appropriate data cut-off is determined for the interim analysis (sufficient to allow completion of data acquisition for the treatment periods contributing to the analysis), analysis files are generated, and analyses conducted by the independent unblinded project statistician for submission to the DSMB.

Upon achievement of the final target sample size for an intervention (111 participants), randomization to that intervention stops. Because interventions may stop at different times in the study, and placebo period data are shared across interventions, care will be taken to observe firewalls that protect confidentiality of data and analysis results for one intervention while other interventions continue to accrue participants. If, for example, data for Intervention A are reported publicly, while the study continues (e.g., A was stopped early for futility), then information about placebo periods included in the

report for A will be limited to comparative group analysis results only. No rare events or within-group event rates that could potentially unblind treatments in the ongoing trial or motivate conjecture about the results of the ongoing interventions will be reported.

Study close-out procedures will not be implemented until all interventions are completed.

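### The mITT set requires post-baseline data on both primary endpoints, so observed data on one endpoint are needlessly dropped from that endpoint's own analysis when the other is missing

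*SAP*

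**What the plan says.** SAP 7.1 sets the analysis population: "The primary and secondary efficacy analyses will be conducted using a modified intention-to-treat (mITT) population". Members must be randomised to the intervention, receive study drug, and "contribute at least one post-baseline measurement for each of the primary endpoints during the treatment period" in which they are randomised to it. Protocol 9.4, under the ITT heading, has the same condition: the participant "contributes at least one post-baseline measurement for each of the primary clinical endpoints". SAP 7.3 carries the rule down to periods: "the treatment periods included in the analyses are limited to those satisfying the respective mITT and per protocol criteria stated above".

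Three other places describe the population without the both-endpoints condition:

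- SAP Section 5 (Power and Sample Size): "All participants randomized to an active intervention or matching placebo will be included in the final efficacy analysis".
- SAP Table 2, the estimand table: "All randomized participants receiving Intervention A during any study period".
- SAP 7.1 on the interim: ITT participants, by biomarker subgroup, "will form the basis for the interim futility analysis".

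SAP 7.4.1 fits an MMRM to each primary endpoint. SAP Sections 2 and 5 count benefit on either endpoint as success, with a Hochberg adjustment.

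**The concern.** Each MMRM needs post-baseline values of its own outcome only. Requiring values of the other outcome as well is a filter on post-randomisation data, applied before the model that SAP 7.4.2 relies on for missing values. It discards primary-endpoint data that were collected.

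One-sided data can occur. In the protocol's schedule of activities (1.3), ACQ-6 may be taken by phone, video or electronic survey. Spirometry needs a device and medication withholds, and a note says that not all procedures will be done at all clinic visits because of COVID-19.

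At stake are some power on the endpoint that was observed, a possible selection effect, and the loss of the same participants from secondary analyses.

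**Working it through.** **1. What the rule does, case by case.** Take a treated participant's active period.

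| Post-baseline data in the period | ACQ-6 model now | FEV1 model now | With an endpoint-specific rule |
|---|---|---|---|
| both | in | in | in both |
| ACQ-6 only | out | out | in for ACQ-6 |
| FEV1 only | out | out | in for FEV1 |
| neither | out | out | out of both |

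Only the two middle rows change. SAP 7.1 applies the same set to secondary efficacy, so an ACQ-6-only participant also leaves the analyses in SAP 7.5 of CompEx, emergency visits, hospital admissions and time to first exacerbation. None of these uses FEV1. Neither document gives an endpoint-specific set.

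**2. How a period reaches a middle row.** The schedule places ACQ-6 and pre-bronchodilator spirometry together at X.2, X.3, X.4 and X.5. An ACQ-6-only period needs at least one ACQ-6 and no FEV1 at any of the four visits. No rate is given, so it is treated below as an assumption q.

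**3. Reproducing the plan's figures.** Inputs are from SAP 5, 7.4.1 and 7.7.1: 111 participants, effect 0.3 SD, correlation 0.70, 10% active discontinuation, 2:1 biomarker positive to negative, interim at 34 + 17, futility cutoff 1.29, biomarker-negative cutoff 1.08, stage weights 0.45 and 0.55, skew-normal reference with parameter 0.32, and Hochberg at one-sided 0.05 and 0.025.

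- Paired standardised effect: 0.3 / √(2 × (1 − 0.70)) = 0.3 / √0.6 = 0.387.
- Evaluable participants: 111 × 0.9 = 99.9.
- Null futility: the statistics for biomarker positives and for all participants correlate √(2/3). The chance that both are below 1.29 is 0.860 per endpoint, and 0.860² = 0.740. The SAP states 0.74.
- Futility when one endpoint has the effect in biomarker positives: 0.143 by simulation. The SAP states at most 0.16.
- Power by simulation (1,000,000 runs): 82.0% if dropping biomarker negatives sends the remaining 111 − 51 = 60 places to positives, and 83.1% if 77 more positives are enrolled as in SAP 7.7.1. The SAP states at least 80%.

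Assumptions not in the documents: the effect is on one endpoint and in biomarker positives only, the other endpoint is null and independent, and biomarker negatives are dropped when both endpoints fall below 1.08.

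**4. Illustrating the loss.** Let q be the share of otherwise evaluable participants with ACQ-6 only, with the effect on ACQ-6. Effective numbers are 99.9 × (1 − q): 94.9 at 5% and 89.9 at 10%. Because the futility analysis is on ITT, the loss was applied in two ways.

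| Power | q = 0 | q = 5% | q = 10% | Fall at 10% |
|---|---|---|---|---|
| 60 further positives, loss in futility and final test | 82.0% | 80.3% | 78.4% | 3.6 points |
| 60 further positives, loss in final test only | 82.0% | 81.1% | 80.1% | 1.9 points |
| 77 further positives, loss in futility and final test | 83.1% | 81.5% | 79.7% | 3.4 points |
| 77 further positives, loss in final test only | 83.1% | 82.4% | 81.6% | 1.5 points |

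If biomarker negatives share the effect, power in the first scenario stays at 87% or above up to q = 15%. Each lost period is credited with full information. A participant with only an early ACQ-6 value tells the model less about the end of the period, so the real loss would be smaller.

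**The case against.** The strongest reply is that the affected group is small. Both measures fall at the same visits, spirometry may be done at home, a second home spirometer is issued for FEV1 (protocol 8.2), and SAP 6.3 leaves X.2 to X.4 to clinic or home. This stands, and it limits the size of the point.

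A single prespecified population is also a defensible convention, and protocol and SAP agree on it. But Hochberg works on the two p-values and does not need the same participants behind both, so the convention gains nothing that offsets the discarded data.

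A reader might infer three stronger claims, which the documents do not support:

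- *Early stoppers are selectively lost and the ACQ-6 result is biased.* Nothing shows that early stoppers tend to have ACQ-6 only. Many may have neither measure, and they would be excluded under either rule. SAP 3.2 describes over-reads as quality control that identifies retraining needs. It does not say that a failed over-read removes the value. No difference between active and placebo, and no direction, can be derived.
- *The study falls below 80% power.* That needs an assumed loss above 5% in the least favourable scenario. With the loss confined to the final test, power stays at about 80% or above at 10%, a share as large as the whole planned discontinuation allowance.
- *The both-endpoints rule causes the conflict with SAP Section 5.* Any mITT that requires study drug and a post-baseline value, including the one proposed here, conflicts with a statement that all randomised participants are analysed. That is a separate wording fault.

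**Conclusion.** The point holds as a cheap improvement to the population definition. The both-endpoints condition is explicit in SAP 7.1 and protocol 9.4, is applied to periods by SAP 7.3, and removes observed data from a model that does not need the other endpoint.

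The number affected is not in the documents and is probably small. A power loss of roughly 2 to 4 points at 10% affected (1.5 to 3.6 across the scenarios shown) is an illustration that rests on an assumed rate and on an effect confined to biomarker positives. It is not an estimate for this trial. Selection on post-randomisation data makes bias possible, but its direction and size are unknown. The mismatch with SAP Section 5 is real and should be corrected on its own account.

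**What to change.** Define the mITT set by endpoint: randomised to the intervention, received study drug, and at least one post-baseline value of the endpoint being analysed in that period. For event outcomes, follow-up time in the period would take the place of a value. Apply the same rule to the period restriction in SAP 7.3 and to protocol 9.4, and keep the both-endpoints set as a sensitivity analysis.

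Separately, reword the SAP Section 5 sentence so that it refers to the mITT population of SAP 7.1.

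The cost is wording in two documents and slightly different denominators for FEV1 and ACQ-6. No new data and no change in sample size are needed. The change should be made before treatment assignments are unmasked for the final analysis. For any intervention with an earlier unblinded review, SAP 1.4 leaves it to the blinded statisticians.
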